6.5 Back-Up Methods if Proportional Hazard Assumption is Violated

The Cox regression relies on the assumption of proportional hazards over time. The hazard proportionality test⁹ is used to check the assumption. If the assumption of proportional hazard is violated. We will use the following backup methods. The log-rank test will be replaced by Kaplan–Meier curve-based tests (including weighted Kaplan–Meier and restricted mean survival time)¹⁰. Survival analysis based on restricted mean survival time will be implemented and restricted mean time lost (RMTL) ratios will replace the hazard ratio for reporting.

6.6 Interim Analysis

We will conduct a pre-specified interim analysis to assess the primary safety and efficacy outcomes after 50% of the planned enrollment population has completed 12-month follow-up. This planned interim analysis will inform the Data Safety Monitoring Board on whether the study should be stopped early due to efficacy, safety concerns, or futility or continue to enroll the full 600-patient cohort. The following three elements are used in considering the interim analysis:

6.7 Stopping for safety:

In the event that three distinct occurrences of unprovoked intracranial hemorrhages or major bleeding episodes are observed within the group of patients receiving apixaban, a thorough investigation will be conducted. This investigation will involve a review by an adjudication committee to confirm the authenticity of these incidents, ensuring that there have been no breaches of the study protocol that could have contributed to the adverse events. If the committee determines that these incidents are indeed linked to the apixaban treatment, specific measures will be implemented in response to these findings.

The decision to take action upon the confirmation of three such events is rooted in the clinical expertise of the researchers involved in the study. This threshold was established after extensive deliberation and consultation with the Mass General–Brigham Institutional Review Board (IRB).

The IRB is an independent body responsible for protecting the rights and welfare of human subjects involved in research, and their guidance plays a crucial role in maintaining the ethical standards of the study.

6.8 Stopping for futility:

The futility stopping rule is in place to prevent the unnecessary continuation of a clinical trial if there is a high likelihood that the primary efficacy outcome rate in the placebo arm falls below 6%. This threshold is considered clinically safe and is set to ensure that resources are not wasted on a trial that is unlikely to produce meaningful results. The problem is framed as a hypothesis testing scenario, where the null hypothesis states that the primary efficacy rate is greater than or equal to 0.06, and the alternative hypothesis suggests that it is less than 0.06.

If the null hypothesis is rejected, it indicates that the actual event rates in the placebo arm are less than 6%. To reject the null hypothesis, fewer than 4 events must be observed. In this context, the trial's progress will be assessed during an interim statistical analysis when the 12-month follow-up is completed for the 300th patient. At this point, if there are fewer than 4 events observed in the placebo group, the decision to terminate the trial will be considered.

6.9 Stopping for efficacy (superiority):

The efficacy stopping rule is a guideline used to determine whether a clinical trial should be terminated early based on the observed results. This rule is applied in situations where the data collected from the trial's participants, in this case, 300 patients, clearly demonstrates that the treatment being studied has a significantly higher efficacy than the placebo. The objective is to avoid exposing more patients to an inferior treatment (placebo) and to expedite the process of bringing a highly effective treatment to the market.

In this specific scenario, the efficacy stopping rule is based on the unadjusted hazard ratio, which is a measure of the relative risk of an event occurring in the treatment group compared to the placebo group. A hazard ratio of less than 0.1 is considered as "overwhelmingly superior efficacy," indicating that the treatment group has a much lower risk of the event than the placebo group.

To determine whether the trial should be stopped, a hypothesis test is conducted. The null hypothesis (H_0) states that the hazard ratio is larger than or equal to 0.1, while the alternative hypothesis (H_1) states that the hazard ratio is smaller than 0.1. If the null hypothesis is rejected based on the data collected from the enrolled patients, it would be concluded that the treatment has overwhelmingly superior efficacy compared to the placebo. As a result, the trial would be terminated early, allowing for a more rapid progression towards making the effective treatment available to patients who could benefit from it.

References

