Study Duration: 36 months; enrollment period of up to 20 months with 12-month follow-up.

Primary Safety and Efficacy Outcomes:

Primary Safety Outcome: International Society on Thrombosis and Haemostasis (ISTH) major bleeding at 12 months.

Primary Efficacy Outcome: Symptomatic, recurrent VTE, defined as the composite of deep vein thrombosis and/or pulmonary embolism at 12 months.

[figure not shown]
Secondary Safety Outcome: ISTH clinically relevant non-major bleeding at 12 months.

Secondary Efficacy Outcome: The composite of death due to cardiovascular cause, nonfatal myocardial infarction, stroke or systemic embolism, critical limb ischemia, or coronary or peripheral ischemia requiring revascularization (major adverse cardiovascular events, including major adverse limb events) at 12 months.

Follow-Up: Follow-up will consist of Electronic Health Record (EHR) review at 12-months from study enrollment.

Interim Analysis: An interim analysis for the primary safety and efficacy outcomes will be performed when 300 subjects have completed 12-month follow-up.

Study Flow Diagram

DVT, deep vein thrombosis; PE, pulmonary embolism; VTE, venous thromboembolism

Figure 1. Study flow-diagram for a single-center, randomized placebo-controlled trial of extended low-intensity apixaban for high-risk provoked VTE.

Study Subject Contact Calendar:

Date	Event	Study Drug
Enrollment (Month 0)	Subject will be consented by study physician and randomized through the Investigational Drug Service computer randomization program.	3 months of study drug (apixaban or placebo) will be given during this visit or sent to subject within 2 business days of the enrollment visit via mail or courier.
Month 3	Study nurse check-in	First 3 months drug containers and unused drug collected via mail and returned to pharmacy for proper disposal, 3 additional months' worth of medication will be given or sent to subject.
Month 6	Study nurse check-in	Drug containers and unused drug collected via mail and returned to pharmacy for proper disposal, 3 additional months' worth of medication will be given or sent to subject.
Month 9	Study nurse check-in	Drug containers and unused drug collected via mail returned to pharmacy for proper disposal, 3 additional months' worth of medication will be given or sent to subject.
Month 12	End-of-treatment visit	All remaining medications, drug containers, and 12-month drug diary will be collected.

Abbreviations and Definitions

Listed in alphabetical order

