The inclusion and exclusion criteria for the current study follows the evidence-based clinical practice guideline recommendations from the ESC and ISTH and identify a population of patients with VTE who have a 3-8% of VTE recurrence per year. We have estimated a 12-month VTE recurrence rate of 6% in our proposed study population, exactly within this range of clinical and research equipoise.

Study Objectives

Primary Safety Objective: To quantitatively assess the International Society on Thrombosis and Haemostasis (ISTH) major bleeding at 12 months.

Primary Efficacy Objective: To quantitatively assess the 12-month rate of symptomatic, recurrent VTE, defined as the composite of deep vein thrombosis and/or pulmonary embolism.

Secondary Safety Objective: To quantitatively assess the 12-month rate of ISTH clinically relevant non-major bleeding.

Secondary Efficacy Objective: To quantitatively assess the composite of death due to cardiovascular cause, nonfatal myocardial infarction, stroke or systemic embolism, critical limb ischemia, or coronary or peripheral ischemia requiring revascularization (major adverse cardiovascular events, including major adverse limb events) at 12 months.

Study Design

600-patient U.S.-based, single-center, randomized, double-blinded, placebo-controlled study of apixaban 2.5 mg orally twice daily for extended prevention of recurrence after provoked VTE in patients with at least one persistent provoking factor who have completed at least 3 months of standard therapeutic anticoagulation and who have a low risk of bleeding.

Study Duration

The study will be completed in 36 months: 2 months for start-up (including Human Research Committee/Institutional Review Board [IRB] approval and finalizing the Case Report Form), 32 months for patient enrollment, follow-up, and data collection, and 2 months for data analysis and writing up the results (**Table 1**).

Table 1. Study timeline.

Milestone	Duration (months)
Start-up	2
Patient enrollment	20
Completion of data collection	12
Data analysis and completion of study report	2
TOTAL	36

Study Population

Patients who are 18 years of age or older with provoked deep vein thrombosis and/or pulmonary embolism, have completed at least 3 months of therapeutic anticoagulation, have a low risk of bleeding, and have at least one persistent provoking risk factor.

Low risk of bleeding is defined by several of the exclusion criteria:

- have contraindications to antithrombotic or antiplatelet therapy

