 - b. Review of relevant laboratory data from within the past three months. If laboratory data for a complete blood count, basic chemistry panel, and coagulation (prothrombin time and activated partial thromboplastin time) are not available from the past three months, these will be drawn at the initial study visit and paid for by the study.
 - c. Serum (β -HCG) or urine pregnancy test (u-HCG) for women of child-bearing potential
7. If the potential study subject does not meet all the inclusion criteria or meets any of the exclusion criteria, the rationale for exclusion from the study will be recorded in the screening section of the electronic case report form (eCRF).

Assessment of Enrollment

After 10 months of study recruitment, an assessment of enrollment will be conducted. If 300 study subjects have not been recruited by 10 months, activation of second study site, Brigham and Women's Faulkner Hospital, will be considered by the Study Investigators. Activation of the Brigham and Women's Faulkner Hospital as a study site will require submission to and approval by the Partners Human Research Committee/IRB.

Treatment Description

Subjects will begin anticoagulation within 3 weeks of passing the screening procedure. Subjects who are 18 years of age or older with provoked DVT and/or PE, have completed at least 3 months of therapeutic anticoagulation, have a low risk of bleeding, and have at least one persistent provoking risk factor will be randomly assigned to receive apixaban 2.5 mg orally twice daily or oral placebo for extended secondary prevention of VTE for a duration of 12 months.

If during the study period the patient requires an invasive procedure or surgery that necessitates the discontinuation of anticoagulation (study drug), apixaban should be held as per the prescribing guidelines (**Appendix**, http://packageinserts.bms.com/pi/pi_eliquis.pdf). If appropriate based on the judgment of the responsible clinician, apixaban should be restarted when safe to do so postoperatively.

Patients and providers will be blinded as to the study group assignment.

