The DSMB will meet to review the safety and efficacy outcomes for the first 300 patients enrolled in the study when they have completed 12-month follow up. Whether to continue, amend, suspend, or terminate the study will be made based in this interim analysis. The DSMB will review the safety and efficacy outcomes again at the completion of follow up completion of the last patient enrolled in the study.

The DSMB will be responsible for:

1. Assessing study enrollment and likelihood of completion of 600 patients randomized
2. Assessing the study event rate in the placebo group and likelihood of obtaining enough events to satisfy the requirements for the primary efficacy analysis
3. Assessing the event rates in the treatment and placebo groups
4. Assessing the accumulated SAEs to determine whether the safety stopping criteria have been met

Actions taken by the DSMB will include the following recommendations:

1. Study termination if stopping criteria for safety or futility have been met
2. Study modification if the DSMB deems that remediation measures have a reasonable probability of successful completion of the study
3. Continuation of the study as is

Blinding/Unblinding

This study will be conducted in a blinded fashion. To maintain blinding of study treatment, study medications will be prepared using placebo matching the active treatments. Subjects, Investigators, members of any of the administrative and adjudicating committees, and the Sponsor's staff conducting the study, will not have access to individual subject treatment assignments.

Blinding is critical to the integrity of this clinical study. However, in the event of a medical emergency or pregnancy in an individual subject, in which knowledge of the investigational product is critical to the subject's management, the blind for that

subject may be broken by the Safety Monitor (or if unavailable, the treating investigator). Before breaking the blind of an individual subject's treatment, the Safety Monitor should have determined that the information is necessary, i.e., that it will alter the subject's immediate management. In many cases, particularly when the emergency is clearly not investigational product-related, the problem may be properly managed by assuming that the subject is receiving active product without the need for unblinding.

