We will conduct a pre-specified interim analysis to assess the primary safety and efficacy outcomes after 50% of the planned enrollment population has completed 12-month follow-up. This planned interim analysis will inform the Data Safety Monitoring Board on whether the study should be stopped early due to efficacy, safety concerns, or futility or continue to enroll the full 600-patient cohort.

The DSMB will be responsible for:

5. Assessing study enrollment and likelihood of completion of 600 patients randomized
6. Assessing the study event rate in the placebo group and likelihood of obtaining enough events to satisfy the requirements for the primary efficacy analysis
7. Assessing the event rates in the treatment and placebo groups
8. Assessing the accumulated SAEs to determine whether the safety stopping criteria have been met

Actions taken by the DSMB will include the following recommendations:

4. Study termination if stopping criteria for safety or futility have been met
5. Study modification if the DSMB deems that remediation measures have a reasonable probability of successful completion of the study
6. Continuation of the study as is

Investigator Responsibilities

Study Initiation

Before enrollment of the first subject at the study site, the following documents must be on file with the funding provider (BMS/Pfizer):

1. Current *curriculum vitae* of the principal investigator and all co-investigators
2. Current, dated Institutional Review Board (IRB) membership list
3. Written documentation of IRB protocol approval (protocol number/title and approval date) and Informed Consent Form (protocol number/title and approval date)
4. A copy of the IRB-approved Informed Consent Form (The Informed Consent Form must be reviewed by the study Principal Investigator prior to IRB submission.)

Study Completion

The following data and materials must be on file at the study site before the study can be considered complete or terminated:

1. Completed electronic case report forms (eCRFs) for all study subjects.
2. All regulatory documents including:
 - a. *Curriculum vitae* for each investigator and study staff member
 - b. Signed confidentiality agreement
 - c. Study protocol and protocol amendments
 - d. Institutional Review Board approval letter(s) for initial protocol and any protocol amendments; as well as continuing review approval letters
 - e. All Institutional Review Board correspondence
 - f. Study termination letter

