Even without the added VTE patient volumes of [name] and [name], we calculate 1600 new and follow-up provoked VTE patients who present for outpatient visits at BWH per year and we conservatively estimate that 25% will fail to meet all the inclusion criteria or will meet at least one exclusion criterion. Therefore, an estimated 1200 patients will be eligible for enrollment in the trial in the first year.

We will also have our research nurse run reports from EPIC to identify other patients in our non-Vascular Medicine cardiology practices that will be eligible but may not be scheduled to see us. We will also aggressively communicate the launch of the study to our non-Vascular Medicine cardiology colleagues. Furthermore, we will recruit from our inpatient cardiovascular medicine consult service and cardiovascular medicine ward service which receive a high volume of provoked VTE. Accordingly, we anticipate having the ability to draw on these additional sources of provoked VTE patients for at least another 100 provoked VTE patients per year.

As the trial will enroll over 20 months, we estimate that we will be able to draw from 1200 patients in the first year and 800 patients in the 8 months that comprise the second year of enrollment. This will yield 2000 patients from which to enroll 600 subjects for the trial.

Based on our prior clinical trial experience at the BWH Thrombosis Research Group, we conservatively estimate that 50% of the patients who are screened and found to be eligible for the trial will consent to participate. Therefore, an estimated 1000 eligible patients would be willing to provide informed consent to participate in the HI-PRO trial. Accordingly, enrollment of the planned 600-patient study population should be feasible and efficiently accomplished at BWH.

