3.1 Target Population

The study is planned to enroll a total of 600 subjects at Brigham and Women's Hospital (BWH). The study design is a single center randomized controlled trial that will take place at BWH. The allocation ratio for the study is 1:1, meaning that half of the participants will be assigned to apixaban 2.5 mg twice daily, and the other half will be assigned to placebo for a duration of one year.

To ensure that the study enrolls the most appropriate participants, a set of detailed inclusion and exclusion criteria have been developed. These criteria are intended to identify individuals who are at high risk of recurrent VTE and are likely to benefit from extended-duration anticoagulation therapy without incurring a prohibitive risk of bleeding.

The allocation of treatments will be conducted by randomization procedures, ensuring that each participant has an equal chance of being assigned to the apixaban or placebo group. The study will be closely monitored for safety, and participants will be closely followed up throughout the study period to assess the efficacy and safety of the treatment. Below, we provide the detailed inclusion and exclusion criteria, which has been described.

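### At the planned accrual the interim look falls at month 22, two months after enrolment ends, so its efficacy and placebo-event futility rules cannot inform whether to keep enrolling

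*Combined protocol and SAP*

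**What the plan says.** The timing is set in several places that agree with one another.

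- Size and accrual: "The study is planned to enroll a total of 600 subjects" (SAP 3.1). The Protocol Summary gives an "enrollment period of up to 20 months with 12-month follow-up", and the Feasibility section repeats the 20 months. Study Duration allots "32 months for patient enrollment, follow-up, and data collection", split in Table 1 into 20 and 12.
- Pace: under Assessment of Enrollment, a second site is considered "If 300 study subjects have not been recruited by 10 months". The DSMB section also treats month 10 as the midpoint of enrolment.
- Trigger: the protocol's Interim Safety and Efficacy Analysis section has the DSMB review "the first 300 patients enrolled in the study when they have completed 12-month follow up". SAP 6.6 and 6.8 give the same trigger as 50% of planned enrolment and as the 300th patient.
- Purpose: SAP 6.6 says that the look informs "whether the study should be stopped early due to efficacy, safety concerns, or futility or continue to enroll the full 600-patient cohort". The protocol uses the same closing words, "continue to enroll the full 600-patient cohort", in item 5 of the DSMB section and in its Interim Analysis section.

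Neither document gives a calendar month for the look or plans a pause in enrolment while the first 300 are followed.

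**The concern.** A look described as choosing between stopping and further enrolment has to happen while patients remain to be enrolled. Here the trigger needs a full year of follow-up on the 300th patient, while the other 300 are planned to enter in the ten months after that patient. Two of the SAP's rules depend on this look: efficacy (6.9) and the placebo event count for futility (6.8). If it comes after the last randomization, neither can spare a patient from being randomized, and the DSMB's listed task of judging whether 600 will be reached is moot by then. The look is also confined to the first 300 patients, although follow-up on the other 300 is accumulating.

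**Working it through.** **Reproducing the plan's timeline.** 2 + 20 + 12 + 2 = 36 months, as in Table 1. 600 / 20 = 30 patients per month, and 300 / 30 = month 10, which matches the protocol's checkpoint.

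**Timing of the look.** Months count from first enrolment. With even accrual over D months, patient 300 enters at D/2, so the look is at D/2 + 12. This precedes D only if D > 24.

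| D (months) | Patients per month | Patient 300 enters | Look | Left to enrol |
|---|---|---|---|---|
| 12 | 50 | 6 | 18 | 0 |
| 20 (plan) | 30 | 10 | 22 | 0 |
| 24 | 25 | 12 | 24 | 0 |
| 26 | 23.1 | 13 | 25 | 23 |
| 30 | 20 | 15 | 27 | 60 |
| 36 | 16.7 | 18 | 30 | 100 |

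The first row is the Feasibility section's ceiling: 1200 eligible per year × 50% consenting = 600 per year.

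**Uneven accrual with a month-20 finish.** A linear ramp-up over the first 3 or 6 months moves the look to month 22.75 or 23.5. For a look before month 20, patient 300 must enter before month 8, at 300 / 8 = 37.5 per month or more, with slower accrual afterwards. On a strongly front-loaded curve (patient 300 at month 5, look at month 17), about 47 patients remain to be enrolled.

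**Person-time under even accrual, ignoring attrition.**

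- Month 22: 300 patients complete, plus 300 with a mean of 7 months: 300 + 300 × 7/12 = 475 person-years. The remainder is 600 − 475 = 125 (21%). A look restricted to the first 300 patients omits 175 of the 475 (37%).
- Month 16: 480 enrolled, of whom 120 are complete and 360 have a mean of 6 months: 120 + 360 × 0.5 = 300 person-years. 600 − 480 = 120 patients (20%) remain to be enrolled.

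**The SAP futility count (fewer than 4 placebo events).**

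- As specified, about 150 placebo patients with 12 months each: binomial P(X ≤ 3) at 6% = 0.019.
- At 300 person-years overall, 150 on placebo, constant hazard −ln(0.94) = 0.0619 per year: expected events 150 × 0.0619 = 9.3, Poisson P(X ≤ 3) about 0.017.
- At month 22 with all patients, 475 / 2 = 237.5 placebo person-years: expected events 237.5 × 0.0619 = 14.7, P(X ≤ 3) about 0.0003.

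**Half the expected primary events.** 300 × 0.06 + 300 × 0.015 = 22.5 in total, so about 11.

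**The case against.** A reader might infer that the look serves no purpose, or that unsafe treatment could not be stopped in time. The documents do not support either reading.

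- Safety: although SAP 6.7 lists safety among the interim elements, the protocol's Safety Stopping Rules apply at any point, and the DSMB reviews safety every three months. The protocol also has a recruitment-based futility rule that is not tied to this look.
- Other aims: SAP 6.8 and 6.9 also seek to avoid needless continuation and further exposure to an inferior arm. At month 22, 300 patients are still in follow-up, so a stop could still serve those aims. Only the enrolment clause fails.

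Three further objections stand as limits.

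- Data capture: the Study Calendar schedules the thrombosis and bleeding evaluations only at 12 months, and the Protocol Summary describes follow-up as record review at that point. Person-time before then is usable only if events are captured and adjudicated sooner. Quarterly calls, admission alerts and the DSMB's reviews of symptomatic VTE provide a route, but not a scheduled endpoint assessment.
- Hazard shape: 300 person-years at month 16 carry the same information as 300 completed patients only if the hazard is roughly constant. The note to the exclusion criteria (risk slow at first, then steeper) and the Sample Size section (recurrence higher nearer the index event) both suggest that it may not be.
- Actual accrual: the documents do not report it. The SAP is dated March 2025, well beyond 36 months after the August 2020 protocol, so recruitment may have been slow enough to give the look some enrolment role.

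**Conclusion.** The point holds for the planned accrual. On the protocol's own figures the look is at month 22 and enrolment closes at month 20, before any time for adjudication or analysis is added. The efficacy rule and the placebo-event futility rule therefore cannot inform whether to continue enrolling, contrary to SAP 6.6 and the two matching protocol statements. Faster even accrual does not help. Slower accrual helps only beyond 24 months, and then modestly (23 patients left at 26 months, 60 at 30). The 24-month limit applies to even accrual; strong front-loading is an exception.

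The effect is limited to enrolment. Safety stopping is intact, and up to 300 patients (about 125 person-years) could still be affected by a stop. The person-time figures rest on even accrual and no attrition. Equating month 16 with the specified look also needs a roughly constant hazard and event capture before the 12-month review. This should be corrected, but it does not threaten the validity of the primary analysis.

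**What to change.** **Preferred.** Trigger the look on information accrued in all randomized patients: for example 300 person-years (about month 16, with about 120 patients still to enrol) or half the expected primary events (about 11). Analyse all adjudicated follow-up to a stated data cut-off with the SAP's time-to-event method, which already handles censoring. Confirm the futility count for the placebo events expected at that look; at about 9 events the present count roughly carries over. The protocol's Stopping Rules for Futility give a different count (36), so the two documents must be reconciled at the same time.

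**If the present trigger is kept.** Include all randomized patients' follow-up and re-derive the count, since 14 to 15 placebo events would be expected at a 6% annual rate and fewer than 4 would almost never occur. Amend SAP 6.6, item 5 of the protocol's DSMB section and the protocol's Interim Analysis section to say that the look concerns ending treatment or follow-up for patients already randomized, not enrolment.

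**Cost.** Changes to the SAP, protocol and DSMB charter, with a short recalculation. The earlier look has fewer patients with complete 12-month follow-up (120 rather than 300) and needs events captured and adjudicated before the 12-month review. Each month between cut-off and decision uses up 30 of the 120 patients, so adjudication must be prompt.
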